5.4 Randomization Criteria

Subjects will be randomized into the study provided they have satisfied all subject selection criteria. Subjects will be stratified according to their Day 0 pre-brushing mean RPI score. The stratification factor will give rise to two strata.

- **Stratum 1 (lower):** mean RPI_{gingival/interproximal} ≥ 0.6 to ≤ 0.8
- **Stratum 2 (higher):** mean RPI_{gingival/interproximal} > 0.8 to 1.0

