12.2 Statistical Methods and Analytical Plan

Additional details of the proposed statistical analysis will be documented in the statistical reporting and analysis plan (RAP), which will be written following finalization of the protocol and prior to study unblinding/analysis (as appropriate).

In this study, baseline is defined as the Day 0 pre-brushing mean plaque score for each index (RPI/TPI). Day 7 and Day 28 pre-brushing plaque levels will also be used to assess plaque removal after single brushing events at these timepoints, noting these values may be influenced by treatment used.

Plaque removal efficacy after first use (change from baseline) will be tested under the null hypothesis:

- H_0 : there is no change from the baseline plaque level;
- H_1 : there is a change from the baseline plaque level.

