12.3.5 Secondary Analyses

Secondary outcome variables include change from baseline in:

- Mean RPI_{overall} (Day 7, Day 28)
- Mean TPI_{overall} (Day 7, Day 28)
- Mean RPI_{gingival margin} (Day 0, Day 7, Day 28)
Sites A, B and C will be used for calculations
- Mean RPI_{inter-proximal} (Day 0, Day 7, Day 28)
Sites D and F will be used for calculations
- Mean TPI_{inter-proximal} (Day 0, Day 7, Day 28)
Mesial and distal sites will be used for calculations

Secondary outcome variables will be derived, based on relevant tooth sites, as the primary outcome variables, with the following summaries generated and analyses performed.

Variable Calculation	Timepoint	Type of Analysis
Actual value	Day 0 (pre- and post-brushing)	Summary statistics

	Day 7 (pre- and post-brushing) Day 28 (pre- and post-brushing)	Plot of pre- and post-brushing values for Days 0, 7 and 30 Box plots
Change from baseline [Day 0 (pre-brushing)]	Day 7 (pre- and post-brushing) Day 28 (pre- and post-brushing)	Summary statistics Plot of change from baseline for Days 7 and 30 ANCOVA for within treatment comparisons

Summary statistics (number of subjects, mean, median, SE, SD, minimum, maximum) will be presented for each outcome variable at each assessment time point by treatment group.

For change from baseline calculations, baseline will be the mean Day 0, pre-brushing plaque score; percent change will also be presented and calculated as $100 \times (\text{Value} - \text{Baseline Value}) / \text{Baseline Value}$. This percent change will be calculated from the aggregated mean levels not at the individual subject level.

Actual mean plaque scores (\pm SE) for both indices will be plotted over time by treatment group. Pre-brushing values will be set at the nominal time recorded (Days 0, 7 and 28); post-brushing values will be set at a small nominal time after (Days 0.5, 7.5 and 28.5). Box plots will also be presented for each outcome variable, over time by treatment group

For variables to be formally analyzed to test for a significant change from zero, change from baseline will be analyzed using an ANCOVA model, with treatment as a fixed effect and the appropriate baseline value as a covariate, as per the primary analysis. For TPI analyses, an extra factor will be included for the RPI_{gingival/interproximal} stratification level (lower/higher). Adjusted mean changes, 95% CIs and p values for change from zero will be presented.

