3.4 Timepoints and Visit Windows

The timepoints and visits for this study are defined in the Section 1-1 “Schedule of Activities” of the protocol and in [Table 1-1](#) of this document. Any deviation from the study schedule may be reviewed on case-by-case basis at the Blinded Data Review Meeting (BDRM) to determine whether the data should be excluded from the analysis populations. A time window non-compliance listing will be produced for the BDRM.

All data included will be by nominal visits and visit windows will not be considered.

4 Data Analysis

Data analysis will be performed by Syneos Health with oversight from GSK CH. The statistical analysis software used will be SAS version 9.4 or higher.

Prior to database closure a BDRM will be conducted in which various aspects of the trial will be discussed and agreed.

Unless otherwise described, all listings will be produced for all randomized subjects.

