4.4.1.2 Statistical Hypothesis, Model, and Method of Analysis

In this study, baseline is defined as the Day 0 pre-brushing mean plaque score for each index (RPI/TPI). Primary analysis will focus on the ability of each study toothbrush to reduce supra-gingival plaque after first use (Day 0, pre- to post-brushing).

Mean RPI_{overall} and mean TPI_{overall} will be calculated for each subject as the total score for all tooth sites assessed divided by the total number of tooth sites assessed. Change from baseline will be derived for each individual tooth site first before calculating the mean overall change for all sites assessed.

Plaque removal efficacy after first use (change from baseline) will be tested under the null hypothesis:

- H₀: there is no change from the baseline plaque level;
- H₁: there is a change from the baseline plaque level.

Change from baseline in mean RPI_{overall} and mean TPI_{overall} will be analyzed using analysis of covariance (ANCOVA).

Change from baseline will be summarized for each primary outcome variable by study product group (adjusted mean change, percent change from mean baseline, 95% confidence intervals [CIs] and p-value for change from zero). Percent change from mean baseline will be derived as: 100 x (Adjusted Mean Change / Mean Baseline Value). Adjusted Mean Change will be derived from ANCOVA model.

No formal sample size has been generated for this methodology development study, thus the p-values will be interpreted with caution.

For analysis of mean RPI_{overall}, the model will include product group as a fixed effect and the baseline mean RPI_{overall} value as a covariate (Table 14.2.2.1.2). RPI stratification level will not be used in the analysis as the actual value will be used as a covariate.

For analysis of mean TPI_{overall}, the model will include product group as a fixed effect, the baseline mean TPI_{overall} value as a covariate and RPI stratification level [lower (defined as Day 0 pre-brushing mean RPI_{gingival/interproximal} ≥ 0.6 to ≤ 0.8) or higher (defined as Day 0 pre-brushing mean RPI_{gingival/interproximal} > 0.8 to 1.0)] as an extra factor (Table 14.2.2.2.2).

Size of effect will be a point of focus. As this is a methodology development study, no adjustments will be made for multiple comparisons.

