4.5.1 Efficacy (Secondary)

The secondary efficacy endpoints are:

- Mean RPI_{overall} (Day 7 pre- and post-brushing, Day 28 pre- and post-brushing)
- Mean TPI_{overall} (Day 7 pre- and post-brushing, Day 28 pre- and post-brushing)
- Mean RPI_{gingival margin} (Day 0 pre- and post-brushing, Day 7 pre- and post-brushing, Day 28 pre- and post-brushing), defined as mean RPI score for sites A, B and C
- Mean RPI_{inter-proximal} (Day 0 pre- and post-brushing, Day 7 pre- and post-brushing, Day 28 pre- and post-brushing), defined as mean RPI score for sites D and F
- Mean TPI_{inter-proximal} (Day 0 pre- and post-brushing, Day 7 pre- and post-brushing, Day 28 pre- and post-brushing), defined as mean TPI score for mesial and distal sites

Secondary outcome variables will be derived, based on relevant tooth sites, as the primary outcome variables.

Summary statistics (n, missing, mean, SD, SE, median, minimum, maximum) of pre-brushing, post-brushing and change from Day 0 pre-brushing will be presented for each secondary outcome variable at each assessment time point by study product group in the following tables:

- [Table 14.2.2.1.1](#) for mean RPI_{overall}
- [Table 14.2.2.2.1](#) for mean TPI_{overall}
- [Table 14.2.2.3.1](#) for mean RPI_{gingival margin}
- [Table 14.2.2.4.1](#) for mean RPI_{inter-proximal}
- [Table 14.2.2.5.1](#) for mean TPI_{inter-proximal}

Change from baseline of secondary efficacy variables will be analyzed using ANCOVA model with product group as a fixed effect and the appropriate baseline value as a covariate, as defined below:

- For mean RPI_{overall}: baseline mean RPI_{overall}
- For mean TPI_{overall}: baseline mean TPI_{overall} and RPI stratification level (lower/higher)
- For mean RPI_{gingival margin}: baseline mean RPI_{gingival margin}
- For mean RPI_{inter-proximal}: baseline mean RPI_{inter-proximal}
- For mean TPI_{inter-proximal}: baseline mean TPI_{inter-proximal} and RPI stratification level (lower/higher)

Change from Day 0 pre-brushing to each analysis time points (Visit 2 Day 0 post-brushing, Visit 3 Day 7 pre- and post-brushing and Visit 4 Day 28 pre- and post-brushing) will be summarized for each secondary outcome variable by product group (adjusted mean change, percent change from mean baseline, 95% CIs and p-value for change from zero) in the following analysis tables:

- [Table 14.2.2.1.2](#) for mean RPI_{overall}
- [Table 14.2.2.2.2](#) for mean TPI_{overall}

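### Does the SAP need a rule for weighting the two RPI strata in the adjusted mean TPI change?

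*SAP*

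**What the plan says.** SAP 4.4.1.2 models change in mean TPI overall on product group, baseline mean TPI overall and the RPI stratum. SAP 4.5.1 uses the same form for TPI overall at Days 7 and 28 and for TPI inter-proximal. Protocol 12.3.5 agrees: "For TPI analyses, an extra factor will be included for the RPI" gingival/interproximal stratum.

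For each brush the SAP reports an adjusted mean change, a 95% CI, a p-value against zero and a percent change. On the adjusted mean it says "Adjusted Mean Change will be derived from ANCOVA model"; on the percentage, "Percent change from mean baseline will be derived as: 100 x (Adjusted Mean Change / Mean Baseline Value". The opening of SAP section 4 adds "The statistical analysis software used will be SAS version 9.4 or higher" but names no procedure or option.

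Protocol 5.4 defines the strata ("The stratification factor will give rise to two strata"), cut at a gingival/interproximal RPI of 0.8. Neither document sets a quota or an expected split.

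For RPI overall the covariate is baseline mean RPI overall, and the SAP says "RPI stratification level will not be used in the analysis as the actual value will be used as a covariate". Protocol 12.3.4 gives the same reason. The stratifying score uses 10 areas per tooth (Protocol 4.1), while RPI overall uses 18 (SAP 4.4.1.1).

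**The concern.** The objectives are within-treatment, so each brush's own adjusted mean is the result. A difference between brushes in an additive model does not depend on how the strata are weighted, but a single-arm mean does. Two analysts following the SAP could report different TPI changes, intervals and percentages from the same data. With unequal strata, equal weighting widens the interval. It also puts a 50:50 mix in the numerator of the percent change, over a baseline mean that carries the observed mix. SAP 4.4.1.2 makes effect size a focus, and the estimates are meant to help design later studies.

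The RPI sentence looks wrong for a different reason. It treats the covariate as the stratifying value, and RPI overall is not that value.

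**Working it through.** **Inputs from the documents.** Four arms of about 20, so 4 × 20 = 80 (SAP 1.4). The TPI model has four arm terms, one covariate and one stratum term, so residual df = 80 − 6 = 74. Plaque removal after one brushing is 30-53% (Protocol 2.1). The documents state no adjusted-mean figure to reproduce.

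**Assumptions.** Lower-stratum share p = 0.1 to 0.5 (results are symmetric about 0.5). Residual SD s = 0.2-0.4. Mean baseline TPI 2-3, with 2.5 for percentages. The correlation r of the stratifying score with baseline TPI is 0-0.9. The squared correlation of stratum with baseline TPI is then R² = r² × φ(z_p)² / [p(1−p)], where φ(z_p) is the standard normal density at the p quantile.

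**Formulas.** Let b be the stratum coefficient.
- Equal-weight minus observed-weight adjusted mean: size |0.5 − p| × |b|. There is no product-by-stratum term, so this is the same in every arm.
- Arm SE at observed proportions: about s/√20.
- SE ratio, equal to observed: √(1 + (20/80)(p − 0.5)² / [p(1−p)(1−R²)]).
- SD of the difference when b is truly zero: |0.5 − p| × s / √(80 p(1−p)(1−R²)).

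Example at 20:80 with R² = 0: 0.25 × 0.09/0.16 = 0.1406, and √1.1406 = 1.068.

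| Split | R² | SE ratio | Difference (1 SD, b = 0), in arm SEs | Same, percentage points |
|---|---|---|---|---|
| 50:50 | any | 1.00 | 0 | 0 |
| 30:70 | 0-0.47 | 1.024-1.044 | 0.22-0.30 | 0.4-1.1 |
| 20:80 | 0-0.40 | 1.068-1.110 | 0.375-0.48 | 0.7-1.7 |
| 10:90 | 0-0.28 | 1.202-1.271 | 0.67-0.78 | 1.2-2.8 |

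A true stratum effect adds 0.02, 0.03 or 0.04 TPI units per 0.1 unit of b at the three unequal splits. With b = 0.2 at 20:80 the shift is 0.3 × 0.2 = 0.06 units, or 100 × 0.06/2.7 = 2.2 points at an assumed baseline of 2.7.

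**Simulation check.** Trials of 4 × 20 (500 per split; b = 0.2, baseline 2.7, residual SD 0.3, within-stratum baseline SD 0.35, baseline gap between strata 0.4, all assumed) gave SE ratios of 1.03, 1.08 and 1.23 at 30:70, 20:80 and 10:90. The shift was identical across arms.

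**Effect on the test against zero.**
- Smallest change: 0.30 × 2 = 0.60. Largest SE: 0.4/√20 = 0.0894. Ratio 6.7.
- Largest change: 0.53 × 3 = 1.59. Smallest SE: 0.2/√20 = 0.0447. Ratio 35.6.
- Worst case with equal weights at 10:90: 6.7/1.271 = 5.3.
- Also taking off a shift of 0.4 × 0.3 = 0.12 (b = 0.3): (0.60 − 0.12)/(0.0894 × 1.271) = 4.2.

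The critical value on 74 df is about 2.0.

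**RPI wording.** RPI overall = (10 × gingival/interproximal mean + 8 × mean of the other areas)/18. At a stratifying score of 0.8 it can run from 8/18 = 0.444 (other areas clean) to 16/18 = 0.889 (other areas all covered). The covariate therefore does not fix the stratum. Protocol 4.2 expects little plaque on the smooth surfaces. If so, the two scores are close to proportional (factor 10/18), and the stated reason is nearly right in substance.

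**The case for a change.** The best case for a change is that the reported number is not fully defined, that single-arm estimates are the purpose of the trial, and that one sentence before unblinding would settle it. Protocol 12.2 leaves such detail to the SAP: "Additional details of the proposed statistical analysis will be documented in the statistical reporting and analysis plan (RAP". Observed-proportion weights are also the more precise choice when strata are unequal.

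The silence stands, and so does the precision point if the split turns out lopsided. (Attachment 1, the list of displays, cannot be read here, so a table footnote may already cover it.) What does not follow is a fault in the plan. Equal-weight least-squares means are the default reading of an ANCOVA adjusted mean, and they estimate a legitimate quantity. Observed proportions are another legitimate choice, and their advantage depends on a split nobody has stated. A rule would also have to name the baseline reference value and the subjects whose proportions count, because some will lack Day 7 or Day 28 scores (Protocol 5.5, 6.8).

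On RPI, the SAP sentence follows directly after the covariate is named, so nobody would fit the wrong model.

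**Conclusion.** No change follows. The weighting is a gap that analysts fill with a standard and valid default. At assumed splits of 30:70 and 20:80 it costs about 2-4% and 7-11% in within-arm SE. With no true stratum effect, the typical difference in percent change is about 0.4-1.7 percentage points. A 10:90 split would give 20-27% and 1.2-2.8 points, but nothing in the documents suggests that split. A true stratum effect would add to the shift.

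The shift in TPI units is the same for every brush, so contrasts are unaffected. Over the assumed ranges, no test against zero changes. The success criterion is a numerical reduction for each brush on both indices, and it is not at risk. SAP 4.4.1.1 and 4.5.1 also tabulate unadjusted means and changes, and SAP 4.4.1.2 already asks for caution with the p-values.

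All sizes rest on the assumed split, residual SD, baseline mean and correlation. The RPI sentence is a wording slip beside a correctly specified model.

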4 STUDY DESIGN

4.1 Overall Design

This will be a single center, 4-week, randomized, controlled, examiner-blind, four-treatment arm, parallel design, clinical methodology development study to investigate the plaque removal efficacy of marketed manual toothbrushes in healthy, dentate subjects. Changes in plaque level will be evaluated after first brushing, after two further single brushing events (Days 7 and 28) and following 7 and 28 days usage (twice daily brushing with assigned toothbrush treatment).

Supra-gingival plaque levels will be assessed using two established clinical measures: the RPI and the TPI. Subjects will abstain from oral hygiene for a period of 12-18 hours prior to each assessment visit. Subjects with Day 0 pre-brushing mean RPI_{gingival/interproximal} ≥ 0.6 will be stratified by their Day 0 pre-brushing RPI_{gingival/interproximal} score (lower: mean RPI

gingival/interproximal ≥ 0.6 to ≤ 0.8 ; higher: mean RPI_{gingival/interproximal} > 0.8 to ≤ 1) and randomized to study treatment (Visit 2).

The mean RPI_{gingival/interproximal} ≥ 0.6 is calculated based on the 10 areas for inter-proximal & gingival margins (A, B, C, D, F – facial and lingual sites) as follow: RPI_{gingival/interproximal} sum score/number of gingival and interproximal sites.

To standardize oral hygiene practice, eligible subjects will complete a lead-in period (minimum 5 days) prior to Visit 2 during which they will brush with the toothbrush and regular fluoride toothpaste provided.

The safety and oral tolerability of each toothbrush will be monitored after first use and over the 28-day usage period by review of reported TEAEs.

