To ensure study subjects demonstrate the required propensity for plaque formation, only subjects with Day 0 pre-brushing mean RPI_{gingival/interproximal} ≥ 0.6 will be randomized to study treatment (Visit 2). Interproximal and gingival margins were chosen due to the unlikelihood that plaque will be present on the smooth surfaces of the tooth due to contact/rubbing with cheeks and tongue. Subjects will be stratified by their Day 0 pre-brushing RPI score (*lower*: mean RPI_{gingival/interproximal} ≥ 0.6 to ≤ 0.8 ; *higher*: mean RPI_{gingival/interproximal} > 0.8 to 1.0) to ensure treatment groups are balanced for baseline supra-gingival plaque levels.

A systematic review of manual toothbrush studies (59 publications with a total of 212 brushing exercises) reported 30–53% plaque removal after a single brushing occasion (depending on the clinical index used) and concluded that bristle tuft arrangement and duration of use contributed to the plaque removal efficacy of a brush. Four marketed manual toothbrushes with differing brush head designs, and therefore anticipated differences in cleaning performance, have been selected for evaluation. The dental profession typically recommend ≥ 2 minutes brushing at least twice daily for good oral hygiene, however, studies reported in the scientific literature indicate brushing duration to be much shorter (working estimate 45 seconds) ([Gallagher et al. 2009](#)). A 1 minute brushing time has been selected for this study as representative of consumer behavior.

The study toothbrushes differ in visual appearance. The level of blindness for this study is therefore described as 'examiner-blind'. Study toothbrushes will be dispensed by trained site personnel who are not involved in clinical efficacy assessment procedures and used by study subjects in the clinical examination area and the examiner won't be allowed in the room during this period. This will ensure the clinical examiner remains blinded to treatment and so avoid bias in the clinical assessments. Clinical examination and product usage areas will be free from mirrors to minimize the visual impact of disclosed plaque on subject brushing behavior.

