12.3.4 Primary Analysis

The main focus of the analysis will be the ability of each study toothbrush to reduce supragingival plaque after first use (Day 0, pre- to post-brushing), as measured by mean RPI_{overall} and mean TPI_{overall}.

Mean RPI_{overall} and mean TPI_{overall} will be calculated for each subject as the total score for all tooth sites assessed divided by the total number of tooth sites assessed. Change from baseline will be derived for each individual tooth site first before calculating the mean overall change for all sites assessed. Changes from baseline will be derived, summarized and analyzed.

Change from baseline in mean RPI_{overall} and mean TPI_{overall} will be analyzed using ANCOVA. For RPI, the model will include treatment as a fixed effect and the baseline RPI_{overall} value as a covariate (RPI_{gingival/interproximal} stratification level (lower/higher) will not be used in the analysis as the actual value will be used as a covariate). For TPI, RPI_{gingival/interproximal} stratification level (lower/higher) will be included as an extra factor. Change from baseline will be summarized for each study treatment (adjusted mean change, 95% CIs and p value for reduction from zero). No formal sample size has been generated for this methodology development study, thus the p-values will be interpreted with caution. Size of effect will be a point of focus. As this is a methodology development study, no adjustments will be made for multiple comparisons.

The assumption of normality and homogeneity of variance in the ANCOVA models will be investigated. Violation of this assumption will be overcome using a suitable data transformation or a non-parametric technique (e.g. Wilcoxon Sign Rank test).

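### Does leaving the randomization stratum out of the RPI ANCOVAs, on the ground that its actual value is the covariate, need correcting?

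*SAP*

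**What the plan says.** Randomization is stratified on the Day 0 pre-brushing mean RPI gingival/interproximal score, cut at 0.8 (Protocol 5.4, SAP 3.2). Protocol 4.1 says this score is "calculated based on the 10 areas for inter-proximal & gingival margins (A, B, C, D, F – facial and lingual sites").

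For the primary RPI analysis, Protocol 12.3.4 states that "the model will include treatment as a fixed effect and the baseline RPI_{overall} value as a covariate", and then that the gingival/interproximal "stratification level (lower/higher) will not be used in the analysis as the actual value will be used as a covariate". SAP 4.4.1.2 repeats the reason: "RPI stratification level will not be used in the analysis as the actual value will be used as a covariate".

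In the secondary models (Protocol 12.3.5, SAP 4.5.1) each regional RPI outcome is adjusted for its own baseline: zones A to C for gingival margin, D and F for inter-proximal. The stratum is again absent, and no separate reason is given. Both TPI models carry the RPI stratum as an additional factor. SAP Table 5-1 does not mention the matter.

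**The concern.** A factor used to restrict randomization is normally carried into the model, or replaced by the continuous variable from which it was cut. The plan claims to do the latter. It does not: no RPI model contains the gingival/interproximal score. The primary covariate adds eight sites per tooth to it, and the regional covariates each drop part of it. If baseline adjustment were materially incomplete, adjusted mean changes could shift with chance imbalance and intervals could be wider than necessary. Size of effect is a declared focus, and the study is meant to inform later designs, so a wrong reason could also be copied forward. The TPI models keep the stratum, which makes the RPI treatment look inconsistent.

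**Working it through.** The plan states no SD, effect size or power, so there is no figure of its own to reproduce. Two questions can be checked: how far the covariate differs from the stratifier, and what adding the stratum would do.

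**1. Overlap, from the definitions alone**

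Let S be the stratifying score (zones A, B, C, D, F on two surfaces: 5 x 2 = 10 sites) and R the mean of zones E, G, H, I (4 x 2 = 8 sites). RPI overall covers 9 x 2 = 18 sites, so with the same surfaces graded:

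RPI overall = (10S + 8R)/18

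- Weight of S: 10/18 = 55.6%. Weight of R: 8/18 = 44.4%.
- At S = 0.8, RPI overall runs from 8/18 = 0.444 (R = 0) to 16/18 = 0.889 (R = 1).
- S = 0.90, R = 0 gives 9/18 = 0.50 (higher stratum). S = 0.70, R = 0.25 gives (7 + 2)/18 = 0.50 (lower stratum).

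So RPI overall does not determine the stratum, and the stated reason is inaccurate. How much this matters depends on how much R varies. Protocol 4.2 expects little: "Interproximal and gingival margins were chosen due to the unlikelihood that plaque will be present on the smooth surfaces of the tooth".

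**2. Effect of adding a term: first simulation**

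Assumed, not in the documents: 4000 trials of 80 subjects in 4 arms, blocked within stratum; S with mean 0.78 and SD 0.10, truncated to 0.6-1.0; correlation of S with the other zones 0.3. RPI overall then correlates 0.72-0.94 with S. The table gives the true SD of one arm's adjusted mean change. Removal percentages are for the stratifying zones and the other zones in turn.

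| Case | Planned model | + stratum | + continuous score |
|---|---|---|---|
| 1. Other zones mean 0.50, SD 0.15; removal 20% vs 70%; residual SD 0.03 | 0.00914 | 0.00905 (-1.0%) | 0.00873 (-4.5%) |
| 2. Other zones mean 0.30; removal 30% vs 50%; residual SD 0.05 | 0.01206 | 0.01208 (+0.2%) | 0.01205 (-0.1%) |
| 3. Other zones mean 0.50; removal 40% in both; residual SD 0.05 | 0.01200 | 0.01201 (+0.1%) | 0.01205 (+0.4%) |
| 4. Other zones mean 0.08, SD 0.05; removal 30% vs 50%; residual SD 0.05 | 0.01144 | 0.01146 (+0.2%) | 0.01148 (+0.3%) |
| 5. As 4, removal 40% in both | 0.01154 | 0.01156 (+0.2%) | 0.01160 (+0.5%) |

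Cases 4 and 5 are closest to what Protocol 4.2 expects, and there both additions make precision very slightly worse. Adjusted means moved by 0.0005-0.0022 on average, under 1% of changes of -0.15 to -0.26.

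In case 1 the model SE goes 0.00771, 0.00724, 0.00673. With the stratum it falls by 1 - 0.00724/0.00771 = 6%, while the true SD falls by 1%. The within-arm SE treats the sampled baselines as fixed, so 95% CI coverage of the population mean change goes 0.903, 0.885, 0.873. In case 4 it stays at 0.948, 0.948, 0.949.

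**3. Second simulation, different assumptions**

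1,500 runs per scenario; S with mean 0.8 and SD 0.10, truncated; R with mean 0.25 and SD 0.03-0.20; correlation of S and R 0-0.5; residual SD 0.08; a direct stratum effect on change of 0-0.05.

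- Correlation of RPI overall with S: 0.97-0.98 at R SD 0.03, down to 0.53-0.78 at R SD 0.20.
- Adding the stratum moves the adjusted mean (about -0.21) by 0.0006-0.0024 on average. The largest shift in any single run was 0.0198, in a scenario with a mean CI half-width of 0.0369.
- The half-width is multiplied by 0.947-1.004. It averages 0.036-0.038 without the stratum, so the interval around -0.21 is far from zero either way.
- Residual df go from 80 - 4 - 1 = 75 to 74, a trivial cost.

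**4. Regional models**

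With zone SD 0.12 and zone correlation 0-0.8 (assumed), the gingival margin baseline (6 of the 10 stratifying sites) correlates 0.82-0.95 with S, and the inter-proximal baseline (4 of 10) 0.53-0.89. Overlap is weakest in the inter-proximal model, yet a separate run of that model with the stratum added changed the true SD by only -0.2% to +0.2%.

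**The case for a change.** The strongest case for acting is that the error needs no assumptions. Protocol 12.3.4 names RPI overall as covariate and, in the same sentence, drops a stratum built from a different score because its actual value is used. The expectation of little smooth-surface plaque helps only the primary model; the regional covariates differ from the stratifier because they omit stratifying zones. Adding the stratum needs no new data, costs one df and would match TPI.

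The wording criticism stands: the covariate shares sites with the stratifier and adjusts for it in part, and a report should describe it that way. The argument for a model change does not stand. The main reason to model a stratification factor is valid comparison between arms under restricted randomization, and no between-brush test is planned: the objectives, the hypothesis and the ANCOVA entry in Protocol 12.3.5 all concern change within a brush. The contrast with TPI has a reason too. A TPI baseline contains no RPI sites, so the stratum carries information there that an RPI baseline already largely holds.

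**Conclusion.** The stated reason is inaccurate, but the model it accompanies is defensible and no change to the analysis follows. The intention is plain: use a continuous baseline RPI instead of a two-level category. Choosing the outcome's own baseline is the natural way to do so.

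Under the assumed values, adding the stratum changes the true precision of an arm's adjusted mean by about 1% at most. It shifts the mean by about 1% of the change or less on average. The continuous score gives a visible gain in only one extreme case, and coverage worsens there. Success requires only that scores fall numerically for every brush on both indices, which neither choice threatens.

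The overlap in sites is certain from the definitions. The magnitudes are not, because the documents give no SDs, correlations or zone-level removal rates. Even so, the two sets of assumptions, spanning correlations from 0.53 to 0.98, agree that the effect is small. This is a clerical slip in a rationale sentence with no analytic gain from altering the models.
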